All study staff are HIPAA and CITI certified and will be trained in the use of the web-based platform. Additionally, all clinical staff conducting telehealth sessions will be oriented to the semi-structured curriculum, and the study coordinator who will also be conducting the intersession coaching will be trained and mentored by a CHLA researcher who has recently conducted a similar study utilizing a cell-phone based app and brief coaching for treatment of adolescents with obesity.

Subject Selection and Withdrawal

Inclusion Criteria

Prospective Group:

Youth age 14-18 who meet criteria for or are currently enrolled in the Empower weight management clinic will be included. These criteria include body mass index (kg/m2) that is either greater than the 99th percentile, or greater than the 95th percentile accompanied by an obesity-related comorbid condition such as hyperlipidemia, pre-diabetes or diabetes, non-alcoholic fatty liver disease (NAFLD), obstructive sleep apnea, or polycystic ovarian syndrome.

Youth will need to speak English but those whose parents' primary language is Spanish will be included.

Retrospective Control Group:

All eligible youth from our EMPOWER clinic patients whose first clinic visit occurred between January 2015 and June 30, 2019, and were 14-18 years old, were included in our control group.

Exclusion Criteria

Prospective Group: (1) significant intellectual or neurodevelopmental disability, ie previous diagnosis of autism spectrum disorder or developmental delay (2) non-English speaking; (3) age < 14 years and > 18 years (4) weight greater than 255 kg.

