Given the shared nature of group appointments, participants should be at approximately the same developmental stage as their peers. Discussion topics may include stigma, body image, family dynamics, and school issues, and therefore a wide variance in age range or cognitive status could potentially diminish the effectiveness of the group sessions. Non-English-speaking youth will be excluded due to limitations in translation services for such a small pilot project. Lastly, with respect to the weight limit, we are excluding patients whose baseline weight is greater than 255 kg, because the scale we use for study visits has an upper weight limit of 272 kg. Because we anticipate that some patients will experience weight gain rather than weight loss, we are allowing for the possibility of a 17 kg weight gain over the 6-month course of the study and therefore choosing an upper weight limit which is 17 kg less than the upper limit of the scale.

Subject Recruitment Plan and Consent Process

If potential subjects are interested in hearing more about the study but unwilling to do so at their in-person Adolescent EMPOWER or other clinical encounter (i.e. outpatient clinics, Emergency Department, Physical Therapy, Occupational Therapy, and Clinical Nutrition), we will obtain their telephone or electronic contact information as well as mailing address, and permission to contact them at a later date and to mail consent forms to their electronic or physical mailing address.

If CHLA Health Network pediatricians have patients that are eligible for the study and would like to be referred, they can forward their patients' information to our study coordinator as per the attached email, and we will screen them by phone with the same recruitment screener.

Waiver of consent is being requested only for retrospective control group subjects. This is due to impracticality of obtaining consents from patients we are no longer following clinically, whereas for the telehealth intervention group, which is a prospective group, we will be obtaining informed consent from all adult participants, given the very interactive nature of the intervention. Written consent will be obtained from all subjects who turn 18 during the course of study participation. Their re-consent will be obtained via the addendum document once they turn 18 on their next visit.

Risks and Benefits

 Some of the questions may make the participant feel uneasy or embarrassed.

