(3) Parents will be contacted on a weekly basis to update them about their child's session attendance, the general content of the sessions, and to remind them to prompt their child to log on to their twice monthly telehealth sessions. We will ask for their preferred mode of contact (text message, email, and/or phone) and use all preferred methods to contact them.

- 4) All Telehealth sessions will be recorded. The recordings may include audio and video (only if the participants have their camera turned on during the session), and video of the research staff running the session. Participants will be reminded verbally before every session that they will be recorded.
 - Data collected on Experimental procedures for the telehealth group include:
 - 1. Data collection from Empower referral packets and/or the electronic medical record regarding their weight/body mass index (BMI), blood pressure, medications, and lab results, onto the CRFs. Date of study visit, and current zip code will be included, as well as preferred contact method for coaching (ie text, mobile phone, or electronic mail). If contact info itself (ie the actual mobile number or electronic mail address) must be updated, it will be documented onto the subject code list and contact info log. Unstructured notes about the telehealth sessions will be documented onto the CRFs by the session facilitator(s) and may include individual participants' level of engagement and involvement during the session, as well as noted significant changes in patient's home circumstances, life events, travel, or major illnesses.
 - 2.Twice monthly weights will be entered into the scale's app will be recorded as well.
 - 3. Missed telehealth sessions will be tallied at the final study visit for each telehealth group participant.
 - 4. Questionnaires assessing quality of life, self-efficacy, diet, and physical activity habits will be administered and collected at baseline, 3-month, and 6-month visits; at the 6-month end point they will also complete a survey about satisfaction with care. It is anticipated that it will take participants 30 to 60 minutes to complete these questionnaires, in addition to a brief visit with research staff to obtain their measurements.

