 - 5.A1C, fasting glucose, fasting lipids, AST and ALT will be drawn at 6-month visit, and results will be documented as well. They will also be drawn at baseline, if participants did not have them performed as part of their clinical care during the previous 6 months. Baseline lab results will also be documented.

6.General session information for bi-weekly (every 2 weeks) telehealth sessions will be collected onto the Telehealth Session Report forms by the session facilitators, including which participants attended and how the facilitator felt the session went.

 Experimental procedures for Control Group subjects will be limited to data abstraction from the CHLA KIDS electronic medical record (EMR

Statistical Plan

As noted previously, the target recruitment of 32 intervention and 176 control was arrived at based on practicality and feasibility for a pilot study. For evaluation of changes in the continuous outcomes, BMI, blood pressure, and hemoglobin A1C, triglyceride level, and ALT, assessed at baseline and immediately following the end of the 6 month intervention, we will utilize regression methods, which will allow us to compare the magnitude of change between the telehealth intervention and the comparison group, taking into account both change from baseline to follow-up time points as well as relevant baseline covariates. For these analyses covariates will be participants' age, gender, and presence of existing medical conditions (e.g. diabetes; rheumatologic conditions) that could affect weight loss.

Update June 2021: Matched control group subjects will be identified by calculating a propensity score, by collecting data for all potential control patients seen in EMPOWER clinic in the approved date ranges. There is no change to the nature of the data points, and their data will be extracted from KIDS and entered into REDCap database as already outlined.

Update Dec 2022: Given the limited data available for each of the matched clinic control patients (many had missing lab and other values), it was determined that we should remove the "matched" inclusion criteria and collect data on all 176 eligible control patients, in order to have a statistically meaningful cohort.

Data Handling and Record Keeping

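### Efficacy and attendance comparisons: telehealth participants may already be in Empower care while controls enter by first Empower visit, and the disability and language exclusions are stated for the telehealth arm only

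*Combined protocol and SAP*

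**What the plan says.** Inclusion Criteria, prospective group: "Youth age 14-18 who meet criteria for or are currently enrolled in the Empower weight management clinic will be included". No limit is set on how long a participant has been in Empower. Subject Recruitment Plan and Consent Process names the in-person adolescent Empower visit among the recruitment settings, so enrolled patients are expected.

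Inclusion Criteria, control group: "All eligible youth from our EMPOWER clinic patients whose first clinic visit occurred between January 2015 and June 30, 2019", aged 14 to 18. The word *eligible* is not explained here, in the opening summary, or in the Statistical Plan, which counts 176 such patients.

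Exclusion Criteria, headed for the prospective group only: "1) significant intellectual or neurodevelopmental disability, ie previous diagnosis of autism spectrum disorder or developmental delay (2) non-English speaking", then age and a weight limit of 255 kg. No exclusion list for controls follows. The language rule concerns the youth, not the family: "Youth will need to speak English but those whose parents' primary language is Spanish will be included". The reason given is practical: "Non-English-speaking youth will be excluded due to limitations in translation services for such a small pilot project".

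Statistical Plan: the regression of change in BMI, blood pressure and laboratory values adjusts for "age, gender, and presence of existing medical conditions (e.g. diabetes; rheumatologic conditions) that could affect weight loss". The December 2022 update drops matching: "Given the limited data available for each of the matched clinic control patients (many had missing lab and other values". The matching factors named in the opening summary were age, gender and severity of obesity; the variables in the June 2021 propensity score are not listed.

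Intervention Visits lists the telehealth data items, among them "Data collection from Empower referral packets and/or the electronic medical record regarding their weight/body mass index (BMI), blood pressure, medications, and lab results". Prior Empower visits are not listed.

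**The concern.** Hypothesis 2 (Rationale for the Selection of Outcome Measures) sets telehealth against in-person care on efficacy; hypothesis 3 does so on attendance. Both need the arms to be alike at baseline apart from mode of delivery, or the differences to be handled in analysis.

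Two differences may go unhandled. First, a telehealth participant may be part-way through Empower care at baseline, while a control may be measured from a first visit. Rationale for this Study says that in-person care succeeds modestly in many patients and fails in some, so enrolled youth who join telehealth could be partial responders or non-responders. Second, controls may include youth with a developmental diagnosis, or who do not speak English, who could not have entered the telehealth arm. If either group changes differently over six months, or keeps appointments differently, the comparison mixes that difference with the effect of telehealth. Without a record of prior Empower visits, the first difference might not even be describable afterwards.

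**Working it through.** **1. The plan's own figure.** The sample size rests on feasibility, with no alpha, power, SD or margin, so there is no power calculation to reproduce. The sums are 30 + 176 = 206 (opening summary) and 32 + 176 = 208 (Statistical Plan).

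**2. Arms side by side.**

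| Feature | Telehealth | Control |
|---|---|---|
| Entry | Meets Empower criteria, or already enrolled | First Empower visit, January 2015 to June 30, 2019 |
| Age | 14 to 18 | 14 to 18 |
| Disability exclusion | Stated | Not stated |
| Youth must speak English | Stated | Not stated |
| Baseline | In-person baseline study visit | Not stated |
| Prior Empower visits | Possible; not a listed data item | None, if baseline is the first visit |

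**3. Control baseline.** Entry closes June 30, 2019 and data close December 31, 2019: 31 + 31 + 30 + 31 + 30 + 31 = 184 days, about six months. This fits a first-visit baseline with a six-month outcome. It is an inference, and patients who entered in 2015 could have more than four years of data.

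**4. Adjustment.** Neither the three regression covariates nor the three stated matching factors include language or prior Empower care. Existing medical conditions might capture a developmental diagnosis.

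**5. Size of bias.** For one factor, bias = (difference between arms in the share with the factor) × (difference in six-month change linked to it). The documents give neither term. The share of telehealth participants with prior Empower care could be anything from 0 to all 32. The one Empower effect reported (Prior Literature) is a mean change of -0.09 in BMI z-score among 109 patients with four or more visits; it does not say how later change varies with earlier care.

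Illustration only, with assumed differences in change of 0.03 to 0.09 z:
- Half the telehealth arm previously in Empower: 0.5 × 0.03 = 0.015 to 0.5 × 0.09 = 0.045 z.
- Language or disability factor in 5% to 30% of controls: 0.05 × 0.03 = 0.0015 to 0.30 × 0.09 = 0.027 z.

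These are not estimates, and the sign is open.

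**6. Precision cost of restriction.** Detectable difference = (1.960 + 0.842) × √(1/n₁ + 1/n₂), in SD of the outcome. Two-sided 5%, 80% power and no covariate adjustment are assumed. The arm of 24 is 2 × 12 from Overview Design Summary. Removing 20% of controls is an assumption: 176 × 0.8 ≈ 141. So is outcome data for only half the controls: 88, and 88 × 0.8 ≈ 70.

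| Controls with outcome | 32 telehealth | 24 telehealth |
|---|---|---|
| 176 | 0.54 | 0.61 |
| 141 | 0.55 | 0.62 |
| 88 | 0.58 | 0.65 |
| 70 | 0.60 | 0.66 |

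For example, 2.802 × √(1/32 + 1/176) = 2.802 × 0.192 = 0.54. A 20% loss of controls costs 0.01 to 0.02 SD.

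**7. Empower-naive subset.** If 18, 12 or 6 of 24 completers were naive (assumed), the detectable difference against 176 controls is 0.69, 0.84 or 1.16 SD.

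**The case against.** **Eligible may already carry the exclusions over.** Clinic, window and age are stated separately, so the word plausibly adds something. This stands as far as it goes: a reader might infer that the populations are shown to differ, and they are not. But the word could equally mean only the clinic's BMI criteria.

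**The exclusions have practical reasons.** Group delivery, translation services and the scale limit do not apply to in-person care, so leaving them off controls may be deliberate. That explains the choice; it does not make the groups comparable. The weight limit probably matters little and is no part of the point.

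**Matching did not cover these factors.** A reader might infer that the December 2022 update opened the gap. The documents do not support that: the stated factors never included language or prior Empower care. What removal clearly lost is severity of obesity, which is a separate matter.

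**Covariates could not repair this.** Non-English-speaking youth are absent from the telehealth arm by design, and prior Empower visits are zero for every control measured from a first visit. Adjusting for a factor with no variation in one arm adds little to restriction. This stands and determines the form of the fix.

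**Many entrants may be new referrals.** The opening summary speaks of referred patients, baseline laboratory values may come from referral packets, and past visits may be recoverable from the medical record. All true, but enrolled patients are expressly admitted, and nothing plans to count them.

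**Conclusion.** The point holds as a possible, unsized bias. As written, the plan may compare youth part-way through Empower care, selected on language and disability, with controls taken from a first visit and without those stated exclusions. The stage-of-treatment difference depends on the control baseline being the first visit; the population difference depends on *eligible* not carrying the exclusions over. The documents settle neither.

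A reader might go further and infer that the comparison favours one arm, or that the study fails. Neither follows: the direction is unknown, efficacy is the tertiary aim of a pilot sized on practicality, and single-arm feasibility results are unaffected. The attendance comparison shares the population difference and has no stated adjusted analysis. This should be corrected because the remedy is cheap; it is not a fatal flaw.

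**What to change.** 1. Define *eligible* for controls. Apply the disability and language exclusions to controls where the chart records them, at least as a sensitivity analysis beside the all-control analysis, and restate the 176 if it changes. Use the youth's own language: a family-language field would remove controls who meet the telehealth rule.
2. State that the control baseline is the first Empower visit, if that is the intent, with follow-up at about six months.
3. Abstract prior Empower visits (yes/no, and number before telehealth baseline) for each telehealth participant from the medical record. Report the share, and give a descriptive comparison limited to Empower-naive participants. Note that Empower-naive is not treatment-naive, because KidsNFitness referrals are admitted.
4. Handle these factors by restriction rather than by added covariates.

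Cost: a few more chart items, some of which will be missing, and possibly a return to charts already abstracted. New control items must fall within the approved data points and the consent waiver, or be added by amendment. The loss of precision is small under the assumptions shown; the Empower-naive comparison is too imprecise to be more than descriptive.

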This is a pilot study that aims to compare treatment for obesity in adolescents delivered via a group telehealth model with treatment provided via our traditional in-clinic Empower weight management program, in order to assess feasibility, cost-effectiveness, and efficacy of group telehealth. We will assess efficacy by measuring: (1) Changes in BMI, blood pressure, and relevant laboratory values (2) Quality of life scores (3) Self-efficacy scores (4) Patient satisfaction. Subject recruitment and study design: Patients that have been referred to Empower and the KidsNFitness program will be eligible, as well as CHLA patients seen in a multitude of environments, including outpatient clinics, the Emergency Department, the inpatient setting seen by Physical Therapy, Occupational Therapy, and Clinical Nutrition. In order to be recruited to the intervention group, participants must be between 14 and 18 years of age; informed consent will be obtained. After obtaining their consent, intervention group participants will be assigned to the intervention telehealth group (final total n=32). We plan to run two consecutive 6-month cohorts. Each cohort will consist of two telehealth groups of 6-8 participants each (total 12-16). We plan to over-enroll each group to account for expected attrition; we will enroll a minimum of 6 and maximum of 8 participants in each of the two telehealth groups, for a total of approximately 30 participants (final total n=32) between the two 6-month cohorts. Parents will be contacted on a weekly basis to update them about their child's session attendance, the general content of the sessions, and to remind them to prompt their child to log on to their twice monthly telehealth sessions. We will ask for their preferred mode of contact (text message, email, and/or phone) and use all preferred methods to contact them. Intervention group subjects will be enrolled into a group telehealth program, in which twice monthly sessions will be held using a HIPAA compliant web-based platform, for 6 months.

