EMPOWER is a multi-disciplinary, team-based clinic model, involving physicians, psychologists, registered dietitians (RDs), and physical therapists (PTs) providing tertiary care management of obesity. Data from the first two years of EMPOWER show that patients with four or more visits (n=109) experienced a decrease in average BMI z-score (-0.09SD). This, though modest, is promising; however, both cost and patient retention present significant challenges to EMPOWER and other tertiary care pediatric obesity programs and may be barriers to further progress. Much administrative personnel time is consumed in working with insurers in order to authorize visits, and nevertheless, this type of hospital-based care is poorly reimbursed. Getting to CHLA is often a major challenge for our patients, due to the large urban sprawl of Los Angeles, traffic, limited and expensive parking, and poor public transportation. Frequent visits result in missed work and school days, a burden to families. Our adolescent patients face even greater challenges, as they they are in the process of learning to manage their own health and balance the emotional and social changes required in the transition to adulthood, with family and parental expectations and limitations.

Rationale for this Study

Telehealth technology presents an innovative, cost-effective, and often highly engaging alternative to in-person visits, which bypasses many of the logistical difficulties of getting to CHLA. Moreover, adolescents today are highly attuned to, and aligned with, digital and mobile technologies, and are natural consumers of media in this format. There is strong evidence from numerous published studies that telehealth can be an effective tool for chronic disease management (1,2, 3). Additionally, many youth with obesity are significantly socially isolated, and our current individual patient-provider model does not effectively address this isolation in the way we expect a group session will; various published studies of group treatment have demonstrated inter-participant support and positive effects of social interaction (4, 5, 6).

While our current model leads to successful weight management in many of our patients, success is often modest, as mentioned above; and for some of our patients, it simply does not work. With this proposal, we wish to pilot a group telehealth model targeted at adolescents with obesity.

Citations:

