
randomized controlled trial examining peer support and behavioral weight loss treatment. Journal of Adolescence. 44:117-123.

Study Objective

Primary Aim -

To pilot a new care delivery model for adolescent patients with obesity, using group telehealth visits

Secondary Aim -

To assess the feasibility of using telehealth with adolescent patients

Tertiary Aim -

To test the efficacy of group appointments using telehealth

Rationale for the Selection of Outcome Measures

- 1. Use of shared medical appointments via telehealth is a feasible, cost-effective care delivery model for adolescents being treated for obesity.
- 2. The efficacy of this model will be comparable to, or better than, standard multidisciplinary in-person visits.
- 3. Attendance to telehealth visits will be better than attendance to standard in-person visits, as measured by no-show rates and same-day reschedules

Study Design

Overview Design Summary

There will be two cohorts for this study, each lasting 6 months. Each cohort will consist of an intervention arm of 12 subjects. We will recruit a minimum of 12 subjects, up to a maximum of 17 subjects in the first cohort and a maximum of 15 in the second cohort, this over-recruitment will attempt to account for possible attrition from the groups.

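### The telehealth arm admits current Empower patients, but the plan neither states, records nor adjusts for Empower care during the 6 months, so the comparison cannot be shown to concern replacement rather than add-on care

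*Combined protocol and SAP*

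**What the plan says.** **Intended contrast.** The opening summary sets out to "compare treatment for obesity in adolescents delivered via a group telehealth model with treatment provided via our traditional in-clinic Empower weight management program". Rationale for this Study presents telehealth as an "alternative to in-person visits, which bypasses many of the logistical difficulties of getting to CHLA". Item 2 of Rationale for the Selection of Outcome Measures reads: "The efficacy of this model will be comparable to, or better than, standard multidisciplinary in-person visits". Study Objective places efficacy third, after piloting the model and assessing feasibility.

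**Who enters the telehealth arm.** Inclusion Criteria: "Youth age 14-18 who meet criteria for or are currently enrolled in the Empower weight management clinic will be included". The opening summary adds: "Patients that have been referred to Empower and the KidsNFitness program will be eligible". It also names outpatient clinics, the Emergency Department and inpatient services as sources. Subject Recruitment Plan and Consent Process mentions approaching patients at in-person Adolescent EMPOWER encounters and taking referrals from network pediatricians.

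**Who is kept out.** There are four exclusions. The first two read "1) significant intellectual or neurodevelopmental disability, ie previous diagnosis of autism spectrum disorder or developmental delay (2) non-English speaking"; the other two are age and weight. None concerns other weight-management care.

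**Controls.** "All eligible youth from our EMPOWER clinic patients whose first clinic visit occurred between January 2015 and June 30, 2019", aged 14-18.

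**What is recorded and adjusted for.** The data items listed under Intervention Visits cover weight and BMI, blood pressure, medications, laboratory results, app weights, missed telehealth sessions, questionnaires and session notes. Empower and KidsNFitness visits are not listed. Statistical Plan: "For these analyses covariates will be participants' age, gender, and presence of existing medical conditions".

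**The concern.** A participant who keeps attending Empower receives the control treatment as well as telehealth, so the 6-month change reflects both. If enough participants do so, and the visits help, the telehealth arm moves towards or past the clinic arm for a reason unrelated to telehealth. The efficacy hypothesis would then look supported, and readers could take the result as grounds for replacing clinic visits when part of the benefit came from those visits.

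This differs from care received before baseline. Adjusting for earlier Empower exposure would not remove the effect of visits made during follow-up. More participants would not help either, because the distortion is a bias and not random error.

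**Working it through.** The documents give no figure on this point to reproduce. The sample size rests on feasibility, and no comparability margin is stated. The check has two parts.

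**1. Is concurrent Empower care possible, and would it be seen?**

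- Entry: current Empower patients are expressly admitted.
- Exclusion: none of the four criteria removes patients receiving other weight-management care.
- Conduct: no available text says that clinic visits stop or continue. Funding source says that standard of care procedures are not part of the study. That puts such care outside the study without saying it is withheld.
- Data: missed telehealth sessions are tallied; clinic visits are not on the list.
- Analysis: covariates are age, gender and existing medical conditions.

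Concurrent care is therefore possible, and under the listed items its extent would stay unknown.

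**2. How large could the effect be?**

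Inputs:

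- *f*: share of telehealth participants who continue clinic care. Not in the documents; assumed anywhere from 0 to 1.
- *C*: clinic effect in controls. Taken as -0.09 BMI z-score, the figure in Prior Literature for patients with four or more visits (n=109). It is uncontrolled, and on the z-score scale, whereas the plan's outcome is BMI.
- *c*: effect that continued clinic care adds to telehealth. Assumed equal to *C* (-0.09), or half of it (-0.045).
- *T*: effect of telehealth alone. Set to 0 to show the worst case for a false finding of similarity.

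Formulas, assuming effects add:

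- replacement contrast = T - C
- expected observed difference = (T + f × c) - C
- bias = f × c

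With T = 0 and C = -0.09, the true replacement contrast is 0 - (-0.09) = +0.09, so telehealth is worse. The observed difference is 0.09 + f × c:

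| f | bias, c = -0.09 | observed | bias, c = -0.045 | observed |
|---|---|---|---|---|
| 0 | 0 | 0.090 | 0 | 0.090 |
| 0.25 | -0.0225 | 0.0675 | -0.011 | 0.079 |
| 0.5 | -0.045 | 0.045 | -0.0225 | 0.0675 |
| 0.75 | -0.0675 | 0.0225 | -0.034 | 0.056 |
| 1 | -0.090 | 0 | -0.045 | 0.045 |

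At f = 0 there is no distortion. At f = 1 with full additivity, a telehealth programme with no effect would look equal to Empower.

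For scale, the 95% half-width with 32 and 176 participants is 1.96 × √(1/32 + 1/176) = 0.38 standard deviations of the change score. That standard deviation is not stated, so the two sizes cannot be put on one scale.

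**The case against.** The strongest reply is that silence about concurrent care is not evidence that it happens. Eligibility also covers youth who only meet Empower criteria, and several recruitment sources lie outside the clinic. Prior Literature describes travel, authorization and retention problems, so few participants may keep attending. This stands. A reader might infer that the trial compares telehealth plus clinic with clinic, or that it cannot answer the replacement question. The documents support neither reading: the first needs every participant to continue, and the second fails if continued care is absent, rare or recorded.

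Three further inferences go too far:

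- That participants are active KidsNFitness patients. The text says only that they were referred to that program.
- That the attendance comparison is distorted. The telehealth side of that hypothesis rests on telehealth sessions, so clinic visits do not enter its count.
- That the cost comparison is distorted. The documents give no cost method on which this could be checked.

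The size is also open to challenge. The -0.09 is uncontrolled. Full additivity is doubtful, since Empower providers run the sessions and the coaching is described as similar to Empower's. One clinic visit would not deliver the full effect. Patients already in treatment may gain less than controls, who are identified by their first visit. These points make the table an illustration and not an estimate.

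Finally, efficacy is the tertiary aim of a pilot, and the consent pages, screener and curriculum were not available and might address concurrent care. That limits the weight of the point. It does not supply the missing data item or analysis.

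**Conclusion.** The point holds in limited form. Current Empower patients may enter the telehealth arm, and nothing in the available documents settles, records or adjusts for Empower care between baseline and month 6. The arm may be a mixture of telehealth alone and telehealth plus clinic, in unknown proportions. As written, the efficacy comparison cannot be shown to concern replacement rather than add-on care.

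If continued care helps, the bias favours the study's own hypothesis. Its illustrative range is 0 to -0.09 BMI z-score. This assumes additive effects, a clinic effect equal to the uncontrolled figure in Prior Literature, and a continuing share anywhere from none to all. The true share may be zero, in which case the concern has no effect on the result. The non-randomised historical control is a separate limitation. The point bears on the tertiary aim and should be corrected before the efficacy result is interpreted.

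**What to change.** 1. Record Empower enrolment status at baseline for each telehealth participant. Abstract from the medical record the dates of any Empower or KidsNFitness visits between the baseline and 6-month visits. The documents do not say whether KidsNFitness visits appear in that record, so this needs checking. Abstraction must precede destruction of the code key, which the protocol schedules for completion of the research.
2. Report the number and share with any such visit. Label the all-participant comparison *telehealth with or without continued clinic care*. State what the plan assumed about concurrent care.
3. Present the efficacy comparison split by Empower enrolment at baseline, which avoids selection on events after baseline. The split is imperfect, because a participant not enrolled at baseline may start Empower later and enrolled participants carry earlier exposure. Show participants with no visit in the window as a sensitivity analysis only, since that subset is defined after baseline.
4. Make no claim from the all-participant result that telehealth can replace clinic visits, unless visits in the window prove absent or rare.

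**Cost.** A few extra fields for about 32 consented participants, from a record the study already uses, and two supportive analyses. Subgroup estimates will be imprecise: if half the arm (16) were in one stratum, the 95% half-width would be 1.96 × √(1/16 + 1/176) = 0.51 standard deviations of the change score, against 0.38 for the whole arm. No change to anyone's care is proposed.
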